10.0 Local Number of Participants

We will recruit up to 120 smokers in order to complete at least 30 participants 20 achieving complete abstinence.

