15.0 Statistical Considerations

15.1 Data Analysis Plan

The goals of this study are: to determine the effect of switching to SREC on biomarkers of exposure and effect (assessed at 4 and 6 weeks); to determine levels of salivary NNN and HPB-releasing DNA adducts in SREC users (assessed in the verified complete switchers at weeks 4 and 6); and to determine important moderators for SREC use and exposure/effect measures.

Demographic and smoking history variables will be summarized and compared to national survey data for the general population of smokers. Baseline covariates will be summarized to inform the comparison data retrieval on non-users of nicotine/tobacco and smokers from recently completed studies. Continuous measures will be summarized by mean (SD), median (range) or other summary measures. The distribution of biomarker and cytokine levels is usually highly right-skewed and will be analyzed in the log scale and reported as geometric means and 95% confidence intervals. Categorical covariates will be summarized by contingency tables.

The primary endpoints are the weeks 4 and 6 for (1) toxicant and carcinogen exposure biomarkers; (2) inflammatory biomarkers; and (3) DNA adducts adjusted for the baseline value. The analysis of our primary endpoints will use linear mixed models to account for potential intra-subject correlation due to repeated measurements at 4 and 6 weeks from a single individual. With two repeat observations, the within subject correlation structure will be compound symmetry. Residual plots and other diagnostic methods will be used to check model assumptions. The mean model for each hypothesis will include the overall mean and an effect for time (4 or 6 weeks). Therefore, our primary analysis for all endpoints will only adjust for the baseline biomarker level (for precision). Due to the multiple biomarkers being tested in this exploratory trial, a reduced alpha level of 0.001 will be used to determine statistical significance for the time effect. An additional analysis will be completed adjusting for important factors such as environmental toxicant exposures, stress and health to determine the effect their inclusion has on the association between group and biomarkers. The secondary endpoints include the amount of product

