used (cigarettes per day, number of e-cigarette episodes and puffs per day and the number of smoke-free days (cigarette avoidance). These outcomes are considered counts and will be analyzed as Poisson or negative binomial variables. Product use by visit will be analyzed by generalized estimating equation (GEE) models, which account for the multiple visits for each individual. Smoke-free days across the entire study period (approximately 42 days) will be analyzed by a Poisson or negative binomial regression. These analyses will include an offset term to adjust for the number of days reported by visit and in total. Covariates will include baseline patient characteristics that may affect patterns of use. Exploratory endpoints include the subjective measures which will be collected up to 6 times during the study period. Measures providing a score will be analyzed using a linear mixed model. The fixed effect is visits. AEs and SAEs (safety endpoints) will be tabulated. Compliance to the assigned treatment is a concern and we are considering the possibility that the non-compliance rate could be as high as 50%, despite our efforts to keep it at low as possible. Complete switching will be biochemically verified; therefore the analysis will be repeated with only those identified as completely switching to SREC. Estimates and confidence intervals of the degree of reduction in outcome variables can be determined for those that successfully switched to the study product. In addition, we will summarize compliance and evaluate the correlation between compliance and baseline covariates to identify potential predictors of treatment compliance. Finally, we will complete a sensitivity analysis that accounts for missing information using multiple imputation with the Markov Chain Monte Carlo (MCMC) method carried out in PROC MI in SAS. Missing values are imputed using regression models developed from baseline covariates. Values can be imputed for both continuous and categorical variables.¹⁰⁴ Following imputation, standard statistical methods can be applied. A final single assessment of time effect will be obtained from combining the results across the imputed datasets using PROC MIANALYZE in SAS.

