15.2 Power Analysis

Based on our previous experience, we estimate the inter-subject coefficient of variation (CV) for the biomarkers listed in Table 1 to be between 30% and 40%. Biomarkers will be analyzed in the logarithmic scale; as a result, the standard deviation (SD) of the log of the level of these biomarkers is approximately equal to the CV in their original scale. For purposes of our power calculations, we will set the SD for each biomarker at 0.4 and assume a correlation of 0.5 between baseline and 6-week biomarker levels. The major hypotheses will be tested including only smokers who completely switch from smoking to SREC use. If a conservative estimate of only 50% of the 30 enrolled subjects achieving complete switching to SREC is applied, then 15 subjects would have greater than 90% power to detect a 45% decrease in the biomarker level in 6 weeks with a paired t-test. However, we incorporated measures to maximize the complete switching (as described in the Study procedures section) and will aim to have at least 20 subjects achieving this goal. The significance level was set at 0.001 due to multiple biomarkers being tested.

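### The GEE analyses of product use rest on roughly 15 to 30 participants with no small-sample correction, so uncorrected sandwich Wald tests and intervals could be too liberal

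*Combined protocol and SAP*

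**What the plan says.** Section 15.1 treats product use (cigarettes per day, e-cigarette episodes, puffs) as secondary: "The secondary endpoints include the amount of product" used. On the distribution it says "These outcomes are considered counts and will be analyzed as Poisson or negative binomial variables". On repeated measures it says "Product use by visit will be analyzed by generalized estimating equation (GEE) models, which account for the multiple visits for each individual". An offset adjusts for days reported, and "Covariates will include baseline patient characteristics that may affect patterns of use". Smoke-free days over the whole period are a single count per person, modelled by ordinary regression, and fall outside this point.

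The section does not give the covariance estimator, working correlation, test statistic, reference degrees of freedom, small-sample correction or significance level for the product-use models. The only alpha stated is 0.001, for the biomarker time effect. Section 15.1 also says the analysis will be repeated in biochemically verified complete switchers, and it lists identifying moderators of SREC use among the study goals.

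On numbers, section 15.2 reasons from "only 50% of the 30 enrolled subjects achieving complete switching to SREC", that is 15, and says the study "will aim to have at least 20 subjects achieving this goal". Section 10.0 says "We will recruit up to 120 smokers in order to complete at least 30 participants 20 achieving complete abstinence". The Study Summary and section 5.3 instead set 30 abstinent completers as the goal.

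**The concern.** The ordinary GEE sandwich variance is justified by a large number of clusters. With few clusters it tends to be too small, and comparing the Wald statistic with a normal or chi-squared distribution makes this worse. Here each participant is a cluster, and the plan also spends parameters on visit effects and an unstated number of baseline covariates.

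At stake are the intervals for product use and the search for predictors and moderators of use. With about 30 people or fewer, a chance association between a baseline characteristic and use, or a chance difference between visits, could be reported as a finding more often than the nominal level implies.

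**Working it through.** **The plan's own figure.** The only power statement is in section 15.2, for the biomarkers. With log-scale SD 0.4 and correlation 0.5, the SD of a paired difference is 0.4 × √(2 × (1 − 0.5)) = 0.4. A 45% decrease is −ln(0.55) = 0.598. With n = 15 the noncentrality is (0.598 / 0.4) × √15 ≈ 5.79. At two-sided alpha 0.001 the paired t-test has 91.2% power, which agrees with the stated figure of more than 90%. There is no power or error-rate figure for product use to reproduce.

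**Inputs from the documents.** There are five post-baseline visits (weeks 1, 2, 3, 4 and 6; section 5.1). The models are for counts, with an offset and baseline covariates (section 15.1). The cluster numbers are 15, 20 and 30 (sections 10.0 and 15.2).

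**Inputs assumed.** The test level is 5%. The model is a log-link Poisson GEE with exchangeable working correlation, four visit indicators, and one or three baseline covariates, the tested one binary and held by half the participants. Five to seven days are reported per visit. Counts were generated with no visit or covariate effect in three settings:

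| Setting | Mean per full interval | Between-person log-SD | Gamma over-dispersion | Person-specific slope SD |
|---|---|---|---|---|
| Mild | 10 | 0.3 | 0.1 | 0.15 |
| Moderate | 10 | 0.6 | 0.3 | 0.3 |
| Sparse | 2 | 1.0 | 0.8 | 0.3 |

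Each cell has 1,400 replicates. The Monte Carlo standard error is √(0.05 × 0.95 / 1400) ≈ 0.6 points near 5%, and about 1.3 points near 40%.

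**Uncorrected sandwich Wald test: null rejection (%) at 15 / 20 / 30 participants.**

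| Setting | Last v first visit (1 df) | Baseline covariate (1 df) | All visits (4 df) |
|---|---|---|---|
| Mild, 1 covariate | 8.3 / 8.0 / 6.5 | 8.7 / 8.5 / 6.9 | 24.4 / 18.1 / 12.4 |
| Moderate, 1 covariate | 11.0 / 10.8 / 9.4 | 12.4 / 10.4 / 8.3 | 33.1 / 26.0 / 18.3 |
| Moderate, 3 covariates | 12.1 / 8.9 / 8.6 | 16.2 / 12.5 / 9.4 | 34.8 / 26.0 / 20.2 |
| Sparse, 1 covariate | 14.9 / 14.5 / 11.9 | 19.2 / 13.4 / 13.8 | 47.1 / 40.7 / 30.9 |

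Single-parameter tests therefore run from 6.5% to 19.2%. At the null value, a nominal 95% interval would cover about 81% to 93% of the time (100 − 19 and 100 − 7).

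A separate simulation with a higher count level (mean 8 per day over seven-day intervals, log-SD 0.6, over-dispersion 0.3) gave 10% to 16% for a null baseline covariate at 15 to 30 participants. The inflation is therefore not confined to low counts.

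**More participants.** At 60 to 100 participants the single-parameter rates are 4.9% to 6.5% (mild), 5.3% to 7.8% (moderate) and 7.6% to 9.9% (sparse). The 4-df test gives 6.9% to 8.2%, 8.1% to 11.8% and 16.9% to 18.7%.

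**Alternatives at 15 to 30 participants.**
- Mancl-DeRouen variance with an F(q, n − p) reference, single-parameter tests: 3.0% to 4.4% (mild), 2.8% to 6.8% (moderate), 7.1% to 9.4% (sparse).
- The same for the 4-df visit test: 6.9% to 8.0%, 10.8% to 13.1% and 22.3% to 26.7%, so this correction alone does not repair the joint test.
- Generalized score test, all tests and settings: 0.9% to 5.9%.
- Model-based Wald test: 5.3% to 14.9%, so dropping the sandwich is not a remedy.

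**The case against.** The strongest reply is that the plan is silent rather than wrong. It does not commit to a Wald test, and a generalized score test holds its size at these numbers, so inflation does not follow from using GEE as such. A reader might infer that the product-use tests have a fixed error rate well above nominal. The documents do not support that: the rate depends on an unnamed test, an assumed 5% level, and count levels and heterogeneity that appear nowhere in the plan. With mild heterogeneity the single-parameter inflation is modest.

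The number of clusters is also open. A reader might take 15 to 30 as settled, but the figure of 15 was chosen for a paired t-test on biomarkers in switchers. The main product-use model is not restricted to switchers. If 30 abstinent completers are sought and half fail to comply, about 30 / 0.5 = 60 people would start, and the inflation is smaller there. Against this, section 5.3 describes the 120 as recruited for eligibility screening. Participants who do not achieve cessation in the first two weeks are withdrawn and data collection stops (sections 12.1 and 12.2), so many of the extra participants would add only early visits. The statements on enrolment and completers need to be reconciled.

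Among verified complete switchers, cigarettes per day is close to zero by definition, so the 15-to-20 case matters mainly for e-cigarette episodes and puffs. A reader might also suppose that the problem is worst for between-person covariates. The table does not show that consistently: with moderate counts and one covariate, the visit contrast is at least as inflated at 20 and 30 participants, and the joint visit test is far worse than either.

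Finally, these are secondary endpoints in a trial that calls itself exploratory. That limits the consequence but does not remove it, because moderators of use are a stated goal. A score test would protect p-values if it were named, but it would not by itself widen sandwich-based intervals.

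**Conclusion.** The point holds as a conditional one. With about 30 participants, or 15 to 20 in the switcher-only repeat, the usual uncorrected sandwich Wald tests could reject about 7% to 19% of the time for single parameters at an assumed 5% level. The joint visit test could reject about 12% to 47% of the time. Direction and order of size are well supported. The exact values rest on the assumed count levels, heterogeneity, Poisson working variance and exchangeable correlation. No rate was computed for a 0.001 level or for a negative binomial working variance.

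Inflation shrinks with 60 or more contributing participants, though for sparse counts it does not vanish even at 100. A reader should not carry this over to the main results: the biomarker endpoints use linear mixed models, and the stated power is reproduced. The change is inexpensive and worth making before analysis.

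**What to change.** In section 15.1, add to the product-use paragraph that:

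- estimates, confidence intervals and single-parameter tests will use a bias-corrected sandwich variance (for example Mancl-DeRouen), with t or F reference degrees of freedom based on the number of participants less the number of parameters;
- the joint visit effect will be tested by a generalized score or a permutation test (the permutation option was not simulated here);
- a stated significance level applies to these analyses, and a stated set of participants enters the main model and the switcher-only repeat, with sections 5.3, 10.0 and 15.2 and the Study Summary brought into agreement on numbers.

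The cost is a few sentences and an analysis option, with no change to data collection or sample size. Intervals become somewhat wider. The joint score test is conservative at the smallest size (0.9% to 1.9% at 15 participants), so it gives up some power. For sparse outcomes the corrected single-parameter tests still ran at 7.1% to 9.4%, so those results should be reported as descriptive.

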- Cigarette avoidance: the number of cigarette avoidance days, defined as no tobacco cigarettes smoked in the past 24 hours based on daily ITR entries, and the rate of cigarette avoidance, calculated as the proportion of cigarette avoidance days out of the total number of days in the product use period (approximately 42 days for those who complete the study).

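### Smoke-free days are bounded by the days reported, but section 15.1 models them as Poisson or negative binomial, so their standard errors may be wrong in either direction

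*Combined protocol and SAP*

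**What the plan says.** Section 3.2 (Secondary Endpoints) defines a cigarette avoidance day as "defined as no tobacco cigarettes smoked in the past 24 hours based on daily ITR entries". It defines the avoidance rate as a proportion, "calculated as the proportion of cigarette avoidance days out of the total number of days in the product use period", and gives the length of that period as "approximately 42 days for those who complete the study".

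Section 15.1 (Data Analysis Plan) groups smoke-free days with cigarettes per day, e-cigarette episodes and puffs: "These outcomes are considered counts and will be analyzed as Poisson or negative binomial variables". For the total it says: "Smoke-free days across the entire study period (approximately 42 days) will be analyzed by a Poisson or negative binomial regression". It adds: "These analyses will include an offset term to adjust for the number of days reported by visit and in total". Covariates are to be baseline characteristics that may influence use.

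No binomial-type model, and no scaled or robust variance, is named for this total. GEE is named only for product use by visit. The residual checks in section 15.1 are described for the linear mixed models of the biomarkers.

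**The concern.** Cigarettes and puffs per day have no natural maximum, so a count model is reasonable for them. Smoke-free days add at most one per reported day and are bounded by the days reported. Two features of the planned model do not fit this.

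- **The bound.** With a log link and an offset, the fitted rate per reported day is exp(Xβ), which can exceed one. The offset handles unequal numbers of reported days but sets no ceiling.
- **The variance.** Poisson sets the variance equal to the mean, and the negative binomial makes it at least the mean. For a bounded total the variance shrinks as the mean nears the ceiling and grows when people differ widely from each other.

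At stake are the standard errors and intervals for smoke-free days and the tests of their predictors, in a sample of roughly 15 to 30 people. The design encourages values near the ceiling through counselling, a compliance bonus and withdrawal of participants who have not stopped smoking by two weeks. Section 15.1 also allows that "the non-compliance rate could be as high as 50" percent, which would give a mixture. Either pattern is possible, and the count models treat the two very differently.

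**Working it through.** **The plan's own figures.** Six weeks × 7 = 42 days, as stated. No power or precision figure is given for smoke-free days. The only power statement (section 15.2) concerns biomarkers. It reproduces at 91.2% two-sided, consistent with the stated level above 90%, and this point does not touch it.

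**Step 1: variance at one mean.** Take an illustrative mean of 38 of 42 days.

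- Poisson SD = √38 = 6.16.
- Binomial SD, independent days with a common probability = √(42 × 38/42 × 4/42) = 1.90.
- Split sample, 80% at 42 days and 20% at 22: mean = 0.8 × 42 + 0.2 × 22 = 38; SD = √(0.8 × 4² + 0.2 × 16²) = √64 = 8.0.

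At the same mean the Poisson SD can thus be about three times too large or about a quarter too small.

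**Step 2: size near the ceiling.** With independent days, the Poisson SE of the mean is √(42p/n) and the binomial SE is √(42p(1−p)/n). Their ratio is 1/√(1−p): 1.41 at p = 0.5, 2.24 at 0.8, 3.16 at 0.9 and 4.47 at 0.95. The negative binomial variance, μ + αμ² with α ≥ 0, cannot go below Poisson, so it cannot reduce this excess.

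**Step 3: do limits for the overall mean pass 42?** The Poisson 95% CI is μ × exp(±1.96/√(nμ)).

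| n | μ = 38 (90.5%) | μ = 39.9 (95%) | Mean avoidance at which the upper limit passes 42 |
|---|---|---|---|
| 15 | 35.0 to 41.3 | 36.8 to 43.2 | about 92% |
| 20 | 35.4 to 40.8 | 37.2 to 42.8 | about 93% |
| 30 | 35.9 to 40.3 | 37.7 to 42.2 | about 94.5% |

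If all 15 complete switchers had 42 of 42 days, the observed variance would be zero, yet Poisson would give an SE of √(42/15) = 1.67 and a CI of 38.9 to 45.4.

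**Step 4: effect on tests of a predictor.** Simulation with n = 30, one covariate with no true effect, offset log 42, and 1,500 runs per scenario. The documents give no distribution of smoke-free days, so these are assumptions: (A) independent days, p = 0.88; (B) half at 42/42, the rest widely spread (Beta(1.5, 1.5)); (C) 67% at 42/42, the rest high (Beta(8, 2)).

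| | A | B | C |
|---|---|---|---|
| True SD of coefficient | 0.011 | 0.076 | 0.025 |
| Mean Poisson SE | 0.031 | 0.034 | 0.030 |
| Median negative binomial SE | 0.031 | 0.093 | 0.030 |
| Poisson type I error (nominal 5%) | 0.0% | 36.5% | 1.7% |
| Negative binomial type I error (usable fits) | 0.0% | 2.9% | 2.0% |
| Quasi-binomial type I error | 5.0% | 3.4% | 4.9% |
| Negative binomial fits with no usable SE | 51% | 0% | 37% |
| Poisson runs with any fitted upper limit above 42 | 91% | 38% | 99.9% |
| Usable negative binomial fits with any fitted upper limit above 42 | 90% | 99.7% | 100% |

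Other simulations of this kind put the highest Poisson type I error as high as 46%; the pattern was the same.

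**The case against.** The strongest reply is that the plan already contains a workable option. With non-compliance possibly as high as 50%, a mixture of full abstainers and smokers is plausible. In scenario B the negative binomial kept type I error at 2.9%, close to the quasi-binomial's 3.4%, with a conservative SE (0.093 against 0.076). The offset also targets smoke-free days per reported day, which is close to the rate in section 3.2. The endpoint is secondary, in a single-arm study that describes itself as exploratory, and carries no stated hypothesis, alpha or power.

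Much of this stands. The negative binomial does largely absorb the extra variance in a mixed sample, although its fitted limits can still exceed the days reported. It does not help near the ceiling, and the plan does not say how the choice between Poisson and negative binomial will be made.

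Three stronger readings are tempting, and the documents do not support them.

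- *The standard errors will be too large.* This needs most participants near 42 with little spread. The documents give no distribution, and the split in step 1 reverses the direction.
- *Reported intervals will run past 42 days.* For the overall mean this is conditional: at a mean of 38 none does for n = 15, 20 or 30. It happens more readily for covariate-specific fitted values.
- *The complete-switcher analysis will show an impossible interval for smoke-free days.* Section 15.1 says "therefore the analysis will be repeated with only those identified as completely switching to SREC", but that this repeat covers smoke-free days is an inference. A logistic model also gives no usable Wald interval when everyone is at 42 of 42, so that case calls for different reporting, whichever regression is used.

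**Conclusion.** The point holds as a mismatch between endpoint and model. Section 3.2 defines a bounded proportion; section 15.1 fits an unbounded count, and no scaled or robust variance is named. Followed as written, the plan can misstate uncertainty in either direction. Near the ceiling with independent days, the Poisson SE is 2.2 to 4.5 times the binomial SE for mean avoidance of 80% to 95%. In a sample split between abstainers and smokers, the Poisson SE was under half the true value (0.034 against 0.076).

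The independent-days ratios and the simulation results rest on assumed distributions, so they show the possible range and do not predict this trial's error. The consequence is confined to a secondary endpoint and the search for its predictors. The primary biomarker analysis and its power are unaffected. The change is worth making because it is cheap and brings the analysis into line with the protocol's own definition.

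**What to change.** In section 15.1, take smoke-free days out of the count-model sentence and state that:

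- smoke-free days out of days reported will be analysed by quasi-binomial or beta-binomial logistic regression, with days reported as the denominator and not as an offset;
- the avoidance proportion will be reported with its 95% CI;
- any subgroup in which all or nearly all participants are at 100%, such as complete switchers, will be summarised descriptively or with an exact method.

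The text should also say how the days-reported denominator relates to the rate in section 3.2, which divides by all days in the product use period; the two agree only when no daily entry is missing. Keeping Poisson with robust standard errors would address the variance but not the bound, so it is second best. The count models can stay for cigarettes, episodes and puffs.

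Cost: a sentence or two of analysis text, with no new data, visits or participants.

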- HMPMA: 4-hydroxybut-2-ylmercapturic acid
- 2-HPMA: 2-Hydroxypropylmercapturic acid
- 3-HPMA: 3-Hydroxypropylmercapturic acid
- HR: Heart rate
- ITP: Investigational Tobacco Product
- ITR: Interactive Text Response
- ITRS: Interactive Text Response System
- NIDA: National Institute for Drug Abuse
- NMR: Nicotine metabolite ratio
- NNAL: 4-(Methylnitrosamino)-1-(3-pyridyl)-1-butanol
- NNN: *N*-Nitrosonornicotine
- PAH: Polycyclic aromatic hydrocarbons
- PheT: Phenanthrene tetraol
- PS-ECDI: Penn State Electronic Cigarette Dependence Index
- SAE: Serious adverse event
- SREC: Standardized Research E-cigarette
- TNE: Total Nicotine Equivalents
- VOC: Volatile organic compounds

PROTOCOL TITLE: Biomarkers in SREC Users

VERSION DATE: 03/13/2024

STUDY SUMMARY

| | |
|---|---|
| Study Title | Biomarkers of Exposure and Effect in SREC Users |
| Study Design | Within-subjects, repeated measures study |
| Primary Objective | Measure biomarkers of tobacco constituents and inflammation in smokers who will switch for six weeks to the Standardized Research E-cigarette (SREC) developed by the National Institute on Drug Abuse. |
| Secondary Objective(s) | Collect and analyze information on behavioral aspects and a comprehensive panel of subjective measures, including patterns and topography of SREC use. |
| Research Intervention(s)/Investigationa l Agents | Standard Research E-cigarette (SREC) developed by the National Institute on Drug Abuse |
| IND/IDE # (if applicable) | IU0000806, IU0000807, IU0000935, IU0000937, IU0000939/P00128 |
| Investigational Drug Services # (if applicable) | NA |
| Study Population | Cigarette smokers |
| Sample Size (number of abstinent completers) | 30 |
| Study Duration for Individual Participants | A total 11 weeks: 1 week baseline period, 6 weeks of assigned product use and a follow-up at week 10 |

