3.3 Exploratory Endpoints

- Scores on subjective measures:
 - *Fagerstrom Test for Nicotine Dependence* (FTND);⁹⁴
 - *Wisconsin Index of Smoking Dependence Motives* is a multidimensional measure of dependence based on theoretically grounded motives for drug use and intended to reflect mechanisms underlying dependence; subscales have been found to be related to smoking heaviness and relapse;⁹⁵
 - *Product Evaluation Scale* is a 7-point Likert-type scale that includes items from the Cigarette Evaluation Scale⁹⁸ and from a scale that was used to evaluate various medicinal nicotine products⁹⁷ to assess psychological reward, satisfaction and aversiveness (Cigarette Evaluation Scale will be used at baseline);
 - *Product Expectancies Scale*;
 - *Drug Effects/Liking Questionnaire*;⁹⁹
 - *E-Cigarette Purchase Task*

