| WEEK | 92 | 91 | 0 | 1 | 2 | 3 | 4 | 6 | 10 |
| Visit window | | 1 week | | | Can be done anytime during the week | | | 1 day, + 3 days | -1 day, + 3 days |
| Biological samples and biomarker measures | | | | | | | | | |
| Alveolar carbon monoxide (CO) | | X | X | X | X | X | X | X | |
| Vital signs | | X | X | X | X | X | X | X | |
| Urine Pregnancy tests* | | X | | X | | | X | X | |
| NicCheck Test (if applicable) | | X | X | | | | | | |
| First morning void urine (for urinary biomarkers according to Aims 1-3) | | | X | | | | X | X | |
| Blood collection (morning, fasting)***** | | | X | | | | X | X | |
| Oral cells | | | X | | | | X | X | |
| Saliva | | | X | | | | X | X | |
| Subjective measures | | | | | | | | | |

PROTOCOL TITLE: Biomarkers in SREC Users

VERSION DATE: 03/13/2024

| | | | | | | | | | |
|--|---|---|---|---|---|---|---|---|---|
| Demographics Questionnaire | x | | | | | | | | |
| Tobacco Use History and Exposure | x | | | | | | | | |
| Nicotine Dependence (FTND)** | | | x | | | | | | |
| E-Cigarette Dependence (PS-ECDI) | | | | | | | | x | |
| Environmental Tobacco Smoke Exposure | | | x | | | | x | | |
| Occupational & Environmental Toxicants | | | x | | | | x | | |
| Brief Medical History | x | | | | | | | | |
| Concomitant Medications | x | | x | x | x | x | x | x | |
| Prime MD | x | | | | | | | | |
| CESD | x | | | | | | x | x | |
| Alcohol Use Questionnaire*** | x | | | | x | | | x | |
| Recreational Drug Use Questionnaire*** | x | | | | x | | | x | |
| Respiratory and Global Health | | | x | x | x | x | x | x | |
| Health Changes Questionnaire | | | x | x | x | x | x | x | x |
| Adverse Events Scale | | | x | x | x | x | x | x | x |
| ITR product use recording | | x | x | x | x | x | x | x | |
| Timeline Follow Back (TLFB)***** | | | x | x | x | x | x | x | |
| Product Evaluation Scale | | | x | x | x | | x | x | |
| Purchasing Task***** | | | x | | | | | x | |
| Drug Effects/Liking**** | | | x | x | x | x | x | x | |
| Tobacco Use Status | | | | | | | | | x |

* Pregnancy tests may also be administered at clinic visits if last menstruation reported being more than 35 days ago.

** All subjects will be evaluated at baseline.

*** Use over the past 30 days at weeks 2 and 6.

**** Regular cigarettes will be evaluated at baseline for all subjects; at the following visits only SREC will be evaluated.

***** To be done if participant reports using other tobacco products on the daily ITR or if there is missing data in the ITRS

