***** At baseline, the cigarette purchase task will be done. At week 6, a product specific purchasing task will be performed.

***** Participants may opt-in to have their blood drawn

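### The visit effect planned for subjective scores mixes a cigarette-versus-SREC difference with change in SREC ratings, and two listed scales have no visit in the schedule

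*Combined protocol and SAP*

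**What the plan says.** Section 15.1 (Data Analysis Plan) gives two sentences on these endpoints. On frequency: "Exploratory endpoints include the subjective measures which will be collected up to 6 times during the study period". On the model: "Measures providing a score will be analyzed using a linear mixed model. The fixed effect is visits". It states no product term, baseline covariate, set of visits, contrast or significance level for them. The 0.001 level in the same section is set for the biomarkers.

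Section 3.3 lists six measures: FTND, the Wisconsin index, the Product Evaluation Scale, the Product Expectancies Scale, Drug Effects/Liking and the E-Cigarette Purchase Task. It adds that at baseline the Cigarette Evaluation Scale takes the place of the Product Evaluation Scale.

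The Table 3 footnotes in section 5.2 say which product is rated. For Drug Effects/Liking: "Regular cigarettes will be evaluated at baseline for all subjects; at the following visits only SREC will be evaluated". For the purchase task: "At baseline, the cigarette purchase task will be done. At week 6, a product specific purchasing task will be performed".

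**The concern.** A visit effect is naturally read as change over time. Here the object being rated changes between Baseline 2 and week 1. If participants like cigarettes more (or less) than SREC, the visit means differ even when their opinion of SREC never moves. A report could then describe SREC appeal as rising or falling over six weeks when the data show only that two products are rated differently. The plan specifies no contrast that would keep these readings apart.

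The second matter is the match between sections. A scale named as an endpoint in section 3.3 but scheduled at no visit in Table 3 would not be collected.

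**Working it through.** **Step 1. Count the collections.** Marks in Table 3 for each measure in section 3.3:

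| Measure | Visits marked | Total | On SREC |
|---|---|---|---|
| FTND | Baseline 2 | 1 | 0 |
| Wisconsin index | no row | 0 | 0 |
| Product Evaluation Scale | Baseline 2, weeks 1, 2, 4, 6 | 5 | 4 |
| Product Expectancies Scale | no row | 0 | 0 |
| Drug Effects/Liking | Baseline 2, weeks 1, 2, 3, 4, 6 | 6 | 5 |
| Purchase task | Baseline 2, week 6 | 2 | 1 |

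The plan's maximum of six is reproduced, by Drug Effects/Liking alone. The product-use period has only five clinic visits and no section 3.3 measure is marked at week 10, so six requires Baseline 2. The plan's own count thus implies that Baseline 2 is a level of the visit factor.

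**Step 2. Can a product term separate the two?** Code product as 0 at Baseline 2 and 1 at the five later visits. That column is the sum of the five later visit indicators. The design matrix has rank 6 with visit alone and rank 6 with visit plus product, so a product covariate adds nothing. The visit effect does split into contrasts. For Drug Effects/Liking, 5 degrees of freedom become 1 (Baseline 2 versus SREC) plus 4 (among SREC visits). For product evaluation, 4 become 1 plus 3.

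**Step 3. How strongly does the overall test respond to product alone?** Take K visits, n participants, a score SD of 1, compound symmetry with correlation r, flat SREC means, and a baseline mean that differs by d. The noncentrality is

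λ = n d² (K − 1) / [K (1 − r)],

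with K − 1 and (K − 1)(n − 1) degrees of freedom.

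Inputs: K = 6 or 5 from Table 3. For n, section 15.2 gives 15 (50% of 30), 20 (the target for complete switching) and 30. Assumed, because the documents give no value for these scores: d, r and two-sided alpha 0.05.

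- K = 6, n = 20, r = 0.5, d = 0.5: λ = 20 × 0.25 × (5/6) / 0.5 = 8.33; rejection 56%.
- Same n, K and r, with d = 0.3, 0.8 and 1.0: 21%, 95% and 99.7%. A simulation of 20,000 datasets at d = 0.8 gave 95.7%.
- K = 5, n = 30, r = 0.5, d = 0.5: λ = 30 × 0.25 × 0.8 / 0.5 = 12; rejection 78%.

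Range at d = 0.5 over n = 15 to 30 and r = 0.3 to 0.7:

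- K = 6: from 30% (λ = 15 × 0.25 × (5/6) / 0.7 = 4.46) to 95% (λ = 30 × 0.25 × (5/6) / 0.3 = 20.83).
- K = 5: from 32% (λ = 15 × 0.25 × 0.8 / 0.7 = 4.29) to 96% (λ = 30 × 0.25 × 0.8 / 0.3 = 20).

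At d = 0.3 the range over both values of K is 13% to 53%.

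**Step 4. The same test on SREC visits only.** With flat SREC ratings it rejected in 4.9% of 20,000 simulated datasets (n = 20, r = 0.5). This is simply the nominal level under a true null.

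**The case against.** The strongest reply is that this is a within-subjects switching study in which usual-brand smoking is the intended comparator. That visit and product coincide at baseline belongs to the design, and the Table 3 footnotes disclose it. A mixed model with visit gives a mean for each visit. Contrasts among weeks 1 to 6 estimate change in SREC ratings, and Baseline 2 against later visits estimates the product difference. Section 15.1 also does not say what the visit test is for. All of this stands. It limits the point to contrasts that are not specified: the data remain usable.

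A reader might infer several stronger things that the documents do not support:

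- *The rejection rates are false-positive rates.* They are not. If cigarettes really are rated differently, rejecting equal visit means is correct. The risk lies in the interpretation.
- *The two product evaluation forms cannot be compared.* Section 3.3 says the Product Evaluation Scale includes items from the Cigarette Evaluation Scale, so a common-item comparison is available.
- *The model fails for FTND and the purchase task.* Section 15.1 gives six only as a maximum and provides for descriptive summaries of continuous measures, so a single FTND score can simply be summarised. The purchase endpoint in section 3.3 is the e-cigarette task, done once, and nothing shows that it was meant to enter the visit model. PS-ECDI, marked only at week 6, is not a section 3.3 endpoint.
- *The topography objective cannot be reported.* The Study Summary speaks of "including patterns and topography of SREC use". Bouts, puffs and e-liquid mass are collected and use is to be modelled, so at most the word is loose.

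Table 3 was read from PDF with visible damage, so a lost row for the "Wisconsin Index of Smoking Dependence Motives" or the Product Expectancies Scale cannot be fully excluded, although the table otherwise reads as complete.

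**Conclusion.** The point holds as a gap in specification for exploratory endpoints. As written, the overall visit test for Drug Effects/Liking and the Product Evaluation Scale combines a product difference with change in SREC ratings. Under the stated assumptions and a 0.5 SD product difference, it would reject about 30% to 96% of the time with no change in SREC ratings at all. The size depends on a product difference, correlation and alpha that the plan does not give. The direction does not: any true product difference feeds the test. The reading that Baseline 2 is included rests on the count of six, because the plan does not say so in words.

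The Wisconsin index and the Product Expectancies Scale are listed endpoints with no visible place in the schedule. The primary biomarker analysis is untouched, as are safety scores, such as CESD, that rate the same thing at every visit.

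**What to change.** In section 15.1:

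- Test the visit effect on post-switch SREC ratings only: weeks 1, 2, 3, 4 and 6 for Drug Effects/Liking, and weeks 1, 2, 4 and 6 for product evaluation.
- Report Baseline 2 versus SREC as a separate contrast labelled as a product comparison. Name in advance the SREC visit or visits it uses, and restrict it to items common to both forms.
- Present the baseline cigarette and week 6 product purchase tasks as a product comparison, not a time effect.
- Summarise FTND descriptively or use it as a baseline covariate.

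In sections 3.3 and 5.2, reconcile the list with Table 3: delete the Wisconsin index and the Product Expectancies Scale, or schedule them.

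The cost is a few sentences of wording and no new data, apart from a small questionnaire burden if the two scales are kept.
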